The hypothesis is that low frequency brain stimulation focused on and around the seizure onset zone will reduce the occurrence of seizures over time. We base this hypothesis on clinical trials and reports on the treatment of seizures reported in the literature. It has been shown that high frequency rTMS, although beneficial in the treatment of patients with depression, can actually cause seizures [28], while low-frequency rTMS has the opposite effect in that it can actually inhibit the occurrence of such seizures. Modulating brain activity is shown to depend on the selection of the frequency used during stimulation [29, 30]. Therefore, and on the basis of this knowledge, we will restrict the brain stimulation process to a low frequency range between 0.5 and 1 Hz rTMS in people with focal and generalized epilepsy, while taking into consideration all the safety guidelines, ethical issues, and required precautions from prior research in the use of TMS technology [31, 32, 33].

The significance of this work is to address the efficacy of the long-term use of rTMS in the treatment of refractory epilepsy patients. Additionally, the integration of multimodal imaging where TMS, MRI, and EEG could provide data not available through DCS or fMRI alone, which in turn can only augment our understanding of brain mapping and brain dynamics. This study will employ a carefully planned low frequency rTMS protocol, with therapeutic sessions over a one-year time frame, with a possible extension phase protocol if initial study is successful.

III. RESEARCH OBJECTIVES

1. To reduce/suppress the number of seizures in patients with medically intractable epilepsy (partial and generalized) with the use of long-term LF-rTMS. Stimulation will be applied with determined seizure onset zone by inverse solutions and 3D software algorithms of analysis of electroencephalographic data. This objective is based on promising rTMS studies that reported reductions in seizure frequency. The primary continuous outcome measures for this aim will be seizure frequency, EEG epileptiform discharge frequency, seizure severity scale, and psychometric testing.
2. Statistical analysis will be conducted using ANOVA and secondary outcome measures will analyze the number of patients whose seizure frequency decreases by at least 50% (e.g., the “responder” threshold used in studies of anticonvulsant efficacy).

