-----------	-----------	---------	----------	------	----------	-------

Repeated TMS at Low Frequencies to Reduce Seizure Occurrence

						Design
1Hz	120%MT	800	5 days/week for 2 weeks 1/week for 1 month 1/month for 11 months	8	3D Source Localization, vertex, and bipolar frontal	double-blinded, sham-controlled
1Hz	120%MT	800	5 days/week for 2 weeks 1/week for 1 month 1/month for 11 months	8	coil will be placed with an angle of 45 degrees with respect to the scalp without direct contact	double-blinded, sham-controlled

Using a single-blinded, sham-controlled design, we will screen patient's age 2 to 80 years with focal and generalized intractable epilepsy. Baseline data will include a detailed seizure diary over 4 weeks, psychometric testing/neuropsychology evaluation, and 20-minute EEG recordings. Each patient will then begin treatment with 14 minute sessions of 1 Hz rTMS or sham rTMS, 120%MT, and 800 stimuli on the position of the calculated 3D source using EEG, MRI, and digitized electrode locations. The protocol will be divided in 3 groups (Groups 1, 2 and 3) as follows:

- Groups 1, 2, and 3: LF-rTMS for 2 weeks (5 days per week for total of 10 days).
- Group 1: protocol total duration: 1 year: LF-rTMS 1 session/week for 1 month (4 days), and LF-rTMS 1 session/month for 11 months
- Group 2: protocol total duration: 1 year: LF-rTMS 1 session/month for 12 months
- Group 3 (placebo protocol, total duration: 1 year): LF-rTMS 1 session/week for 1 month (4 days); and LF-rTMS 1 session/month.

During each session EEG will be recorded. Also, we would update number of events and frequency data from ongoing seizure diary. Psychometric testing will be performed at the beginning of study, 3 months, and at the end of the study. Thus, each patient will have rTMS testing, psychometrics, and EEG recordings.

Goal recruitment will be 90 medically refractory participants, with 30 participants for each of the three groups, based on the following:

- At least 3 seizures in one month
- No status epilepticus for 1 year
- No change in medication for 1 month

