Statistical analysis will be conducted using SPSS 14.0 software. The baseline seizure frequency and seizure frequency change after treatment will be computed from average weekly seizure frequencies before and after rTMS treatment for each patient. A patient data will be categorized into two treatment groups: rTMS treated and placebo groups.

VII. DESCRIPTION OF WRITTEN CHILD/ADULT CONSENT PROCESS

At a potential subject's visit to the physician's office or hospital, the investigator(s) will provide a comprehensive explanation of the purpose, procedures, possible risks/benefits of the study, and participant responsibilities, and discuss the fact that his/her participation is voluntary, that he/she may withdraw from the study at any time, and that the decision not to participate or to withdraw will not affect his/her regular medical care. Potential participants or their surrogates will be given ample opportunity to ask questions and to consider their decision. If the subject or the surrogate agree to participate, then a signed and dated written informed consent will be obtained.

A copy of the consent form will be given to the participant or the surrogate, and another copy will be placed in the subject's medical record. The informed consent form will be obtained by the investigators listed to perform informed consent procedures.

VIII. EXTENSION PHASE

If the results from this study demonstrate significant medical improvement, patients will be offered an extension phase where they could continue receiving the same parameters of stimulation for one to two additional years at no expense

REFERENCES

- [1] M. Kobayashi and A. Pascual-Leone, "Transcranial magnetic stimulation in neurology," *Lancet Neurology*, vol. 2, pp. 145-156, Mar 2003.
- [2] M. Hallett, "Transcranial magnetic stimulation and the human brain," *Nature*, vol. 406, pp. 147-150, Jul 13 2000.
- [3] P. M. Rossini and S. Rossi, "Transcranial magnetic stimulation: diagnostic, therapeutic, and research potential," *Neurology*, vol. 68, pp. 484-8, Feb 13 2007.
- [4] H. R. Siebner, G. Hartwigsen, T. Kassuba, and J. C. Rothwell, "How does transcranial magnetic stimulation modify neuronal activity in the brain? Implications for studies of cognition," *Cortex*, vol. 45, pp. 1035-1042, Oct 2009.

Repeated TMS at Low Frequencies to Reduce Seizure Occurrence

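### Read together, Sections III, 5.3 and VI imply a 60 v 30 ANOVA with a pooled variance; a method that tolerates unequal spread should be named (minor)

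*Combined protocol and SAP*

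**What the plan says.** The analysis has to be assembled from three places in the combined protocol and SAP.

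- **Section III, item 2** gives the method: "Statistical analysis will be conducted using ANOVA". It does not say which groups enter. Item 1 lists four primary continuous outcomes: seizure frequency, EEG discharge frequency, seizure severity and psychometric testing.
- **Section 5.3** gives the design: 90 participants, "with 30 participants for each of the three groups". Group 2 is described as "Group 2: protocol total duration: 1 year: LF-rTMS 1 session/month for 12 months" and Group 3 as "Group 3 (placebo protocol, total duration: 1 year"). Group 1 has an LF-rTMS schedule with a weekly phase followed by monthly sessions.
- **Section VI** gives the grouping: data are "categorized into two treatment groups: rTMS treated and placebo groups". It also defines the seizure outcome: "seizure frequency change after treatment will be computed from average weekly seizure frequencies before and after rTMS treatment for each patient".

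No section mentions an unequal-variance test, robust standard errors, a check of variances, a transformation or a count model. No SD, alpha, power or effect size is given.

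**The concern.** ANOVA estimates one variance from all groups. When two groups are the same size, the resulting standard error of their difference is right even if the spreads differ. Merging two groups of 30 into one of 60 removes that protection. The pooled variance is then weighted about 2:1 towards the rTMS side, while the true standard error depends mostly on the smaller placebo group.

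Equal spread cannot be taken for granted. The trial enrols focal and generalized epilepsy, sets a minimum seizure count at entry but no maximum, and merges two maintenance schedules. A treatment that reduces seizures, or that works in some patients and not in others, can change the spread as well as the mean. The p-value and any confidence interval for the rTMS-placebo difference would then be somewhat too optimistic or too cautious. Nobody could say which beforehand, and a change of method after seeing the data would look selective.

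**Working it through.** **1. The plan's own figures.** 3 x 30 = 90, which agrees with the recruitment goal. Merging Groups 1 and 2 gives 30 + 30 = 60 against 30. There is no power calculation to reproduce. The 60 v 30 split is not printed. It also rests on Group 2 being active, which is inferred because only Group 3 is labelled placebo.

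**2. Pooled against true standard error.** With n1 = 60 (rTMS), n2 = 30 (placebo) and SDs s1 and s2:

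- pooled: V_p = {[59 s1² + 29 s2²]/88} x (1/60 + 1/30)
- true: V_t = s1²/60 + s2²/30
- ratio of standard errors = √(V_p/V_t)

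The SDs are assumed, since the documents give none.

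- *Placebo SD 1.5 times the rTMS SD (s1 = 1, s2 = 1.5).* V_p = (59 + 65.25)/88 x 0.05 = 1.412 x 0.05 = 0.0706. V_t = 0.0167 + 0.0750 = 0.0917. Ratio √(0.0706/0.0917) = 0.878, so the standard error is about 12% too small.
- *The reverse (s1 = 1.5, s2 = 1).* V_p = (132.75 + 29)/88 x 0.05 = 1.838 x 0.05 = 0.0919. V_t = 0.0375 + 0.0333 = 0.0708. Ratio 1.139, so about 14% too large.
- *30 v 30.* V_p and V_t are algebraically equal, so the ratio is 1.00 whatever the SDs.

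**3. What this would do to a test.** If the means were equal and only the spreads differed, the two-sided error rate at a nominal 5% (assumed; the plan states no alpha) would be 2[1 - Φ(1.96 x ratio)]. That is 8.5% in the first case and 2.6% in the second. Simulation with normal data agrees, and over rTMS/placebo SD ratios from 0.5 to 2 Welch's test stays at 4.8-5.1%. If the two distributions are identical, ANOVA keeps its 5%.

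**4. The outcome the plan names.** Section VI analyses change, so the relevant spread is that of post minus pre. A proportional fall in seizures shrinks post-treatment values. It also makes patients with high baselines change more, which adds spread to the change scores and offsets the shrinkage. The assumptions were lognormal weekly frequencies, log-SD 0.6-1.0, pre-post correlation 0.5-0.9 on the log scale, and a 30% or 50% reduction on rTMS. The rTMS/placebo SD ratio of change then runs from about 0.84 to 1.25. Coverage of the 95% interval:

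| Outcome analysed | ANOVA | Welch |
|---|---|---|
| Change in weekly frequency | about 93.4-96.1% | about 94.9-96.1% |
| Raw post-treatment frequency, log-SD 0.6, 30% / 50% reduction | 92.1% / 88.5% | 94.4% / 93.6% |
| Raw post-treatment frequency, log-SD 1.0, 30% / 50% reduction | 92.1% / 87.8% | 92.7% / 90.6% |

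The last two rows show what would happen if raw frequency were analysed instead, which is not what Section VI describes.

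**The case against.** The strongest reply is that the effect is small on the plan's own outcome. That stands. A reader might infer from the raw-frequency rows that the planned interval would cover only 88-93%, or that it would be systematically too narrow. The documents do not support this, because Section VI defines the outcome as change. There the shortfall is at most about 1.6 points (95 - 93.4), and in some settings the ANOVA interval is slightly too wide.

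Second, the 8.5% and 2.6% error rates need equal means with SDs that differ 1.5-fold. A proportional fall moves the mean too, so these rates illustrate the mechanism and do not predict this trial's false-positive rate. This stands.

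Third, no single section specifies a two-group ANOVA. Section III names the method without groups, and Section VI names the groups without a test. A three-group ANOVA is possible, and its overall F test holds at about 5.0-6.1% over active/placebo SD ratios of 0.5-2. This stands in part. Section VI does ask for two categories, and even inside a three-group ANOVA the contrast of the averaged active groups with placebo has nearly the same distortion (ratio 1.138 when the active SD is 1.5 times the placebo SD).

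Fourth, a reader might assume that all four primary outcomes are affected. The grouping sentence follows text on seizure frequency only, so extending it to the others is inference.

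Fifth, the plan does not promise a confidence interval. True, but the same standard error sets the p-value.

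**Conclusion.** The point holds in a limited form. On the natural joint reading of Sections III, 5.3 and VI, the rTMS-placebo comparison is 60 v 30 with a pooled variance, and it lacks the protection that equal groups would give. If the spreads differ, the standard error is wrong in a direction that cannot be predicted: about 12% too small or 14% too large at an SD ratio of 1.5 one way or the other. For change in weekly seizure frequency the likely consequence is modest and of either sign.

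This rests on Group 2 being active, on ANOVA meaning the ordinary equal-variance form, and on assumed SD ratios and lognormal frequencies, none of which the documents state. It does not show that the planned test is invalid when rTMS has no effect at all. Minor priority: worth correcting because the correction is nearly free.

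**What to change.** Add one sentence to Section VI: the rTMS v placebo comparison of seizure frequency change, and of any other continuous outcome analysed in these two groups, will use Welch's test and confidence interval, or heteroscedasticity-robust (HC3) standard errors when covariates are fitted. The same sentence should confirm that Groups 1 and 2 together form the rTMS-treated category.

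The cost is about 1% in interval width if the spreads are in fact equal. Group sizes, schedules and data collection do not change. The sentence does not deal with skewness: on raw frequency at log-SD 1.0, Welch itself covers only 92.7% and 90.6%. If skewed frequencies are expected, that needs a separate decision.
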